According to the World Health Organization (WHO), chronic obstructive pulmonary disease (COPD) is the third leading cause of death worldwide, causing 3.23 million deaths in 2019 .[1] The most common root cause of COPD in the United States is cigarette smoke and COPD affects more than 15 million Americans. There are approximately 1.5 million emergency department visits, 700,000 hospitalizations, and 150,000 deaths per year in the United States due to COPD. It is the fourth leading cause of hospital readmission with 20-25% of cases lead to readmission within 30 days of discharge.[2-5] Despite significant decreases in mortality over the last 20 years due to reduction of smoking, it was still the fourth leading cause of death in US in 2019.[4,6] The data on the impact of COPD for 2020 and 2021 is somewhat skewed due to the impact of COVID-19 but for both years it is considered the 6th leading cause of death in the US.[7,8]

A key factor in the high morbidity and mortality of COPD is that it is a progressive and irreversible disease characterized by a limitation of airflow due to a combination of damage to the small airways (bronchiolitis) and parenchyma of the lung (emphysema) due to chronic inflammation. Progression of the disease and the irreversible damage to the lower respiratory tract leads to increasing episodes of acute exacerbations of COPD (AECOPD) during which there is a sustained increase in cough, sputum production, and shortness of breath. AECOPD can be self-limited but can also lead to progressive respiratory failure.

One cause of COPD progression is *Pneumocystis jirovecii* (PJ), a fungal pathogen best known for causing pneumonia in patients with HIV or other forms of immunosuppression. PJ is not typically found in the respiratory tract of healthy adults but is highly prevalent in those with severe COPD, particularly those with AECOPD, and the inflammation caused by PJ has been shown to lead to progression of COPD.

Detection of PJ generally requires a bronchoalveolar lavage (BAL) to sample the lower respiratory tract and then use direct fluorescent antibodies (DFA) to stain the sample for the presence of PJ. In the COPD population, a BAL is often too invasive for their tenuous respiratory status and DFA has very low sensitivity for PJ (~20%).

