The standard treatment for PJ is trimethoprim-sulfamethoxazole (TMP-SMX), an FDA approved, inexpensive antibiotic with a well-established safety profile. Despite the large body of evidence pointing toward PJ as a cause of COPD progression and a factor which leads to AECOPD, there has never been a trial of therapy for PJ in the COPD population. Such studies are difficult due to the invasive nature and low sensitivity of standard testing for PJ in this population. Using a highly sensitive PCR based assay, we can easily and safely test the sputum of COPD patients to identify carriers of PJ in order to include them in a clinical trial.

We hypothesize that adding TMP-SMX to standard of care treatment of AECOPD in patients who are colonized with PJ will improve the clinical outcome for the patient. **We further hypothesize** that TMP-SMX can eradicate colonization with PJ. This proposal seeks to confirm our hypothesis through the following two specific aims:

Aim 1: Determine if there is clinical improvement in COPD patients colonized with PJ treated with standard of care plus TMP-SMX vs standard of care plus placebo.

Rationale: For each participant we will determine time to return to baseline oxygen needs, need for mechanical ventilation during the index admission, length of stay, COPD assessment test, time to next admission for AECOPD and number of readmissions for AECOPD in the following 3 months.

Aim 2: Determine the persistence of colonization with PJ in AECOPD patients treated with standard of care plus TMP-SMX vs standard of care plus placebo.

2.1 Determine if TMP-SMX eliminates PJ at end of TMP-SMX therapy and the durability of clearance
2.2 Determine the duration of PJ colonization after standard of care treatment for AECOPD

Rationale: For each participant we will assay for the presence of PJ using PCR on sputum at end of therapy, 1 month and 3 months.

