Multiple studies have confirmed high rates of PJ colonization in COPD patients, and the highest rates are seen in patients with AECOPD.[20] During the clinical trial of the Unyvero system for lower respiratory infections at Beaumont, we found 8 patients out of nearly 500 total patients in the study who were positive for PJ. Of note, HIV patients, who are at the highest risk for PJP, were excluded from that study. Two of the 8 patients had other classic risk factors for PJ pneumonia (transplant and leukemia), the remaining 6 patients all had severe COPD and two of them were so severe that they entered hospice. These findings were what led us to conclude that the association of PJ with COPD was clinically significant and led to the design of this trial.

Through this study we hypothesize that we will be able to show that the simple addition of TMP-SMX to the standard treatment regimen for AECOPD will lead to clinical benefit. If our hypothesis is confirmed larger trials of therapy designed to treat AECOPD and to prevent acceleration of the disease process would be possible. TMP-SMX is a proven, safe, and inexpensive antibiotic, the addition of TMP-SMX as a treatment for AECOPD would be both safe and cost-effective. More importantly, using the paradigm of AIDS patients, prophylaxis with a single daily tablet of TMP-SMX can nearly eliminate the incidence of PJ pneumonia.[24] Further clinical trials could compare if daily TMP-SMX could significantly reduce AECOPD. A reduction in AECOPD of even 5% would represent a huge improvement in clinical care and significant savings to the cost of healthcare.[25]

The low cost, safety profile, and ease of availability of TMP-SMX makes this a therapy that could be applied worldwide even in the lowest resource areas.

Innovation

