
• Carries the diagnosis of COPD and admitted for and admitted with AECOPD to Beaumont, Royal Oak
• AECOPD requires increased cough, increased sputum production, and shortness of breath +/- increased oxygen needs from baseline• Able to produce a sputum sample• Men or women, age ≥40 and <90• Previously enrolled in the EPIC study and PJ detected in their sputum• Currently treated with steroids• Kidney function not severely impaired ($\text{CrCl} \geq 60$)• AST and ALT $\leq 5x$ Upper limit of normal• Willing and able to provide consent to the study	
• Currently diagnosed with pneumonia or COVID• Allergy or hypersensitivity to TMP-SMX• Current ICU admission or mechanical ventilation• Active cancer or chemotherapy (except non-melanoma skin cancer)• Other potentially confounding pulmonary diagnosis• HIV, leukopenia, neutropenia or other immunosuppressive condition or current use of immunosuppressive medications• Presence of gastrointestinal tract abnormalities that would prevent absorption of medications• Patients with concomitant infection requiring antibiotics active against PJ• Concomitant use of coumadin, phenytoin, pioglitazone, repaglinide, rosiglitazone, glipizide or gliburide• Megaloblastic anemia due to folate deficiency• Pregnancy• Expected life span less than 3 months

Table 1: Inclusion/Exclusion Criteria

3 attending physicians, 3 fellows, and 2 residents available to consent. In addition, a nurse coordinator experienced at consenting will be available to consent or assist the physicians with consenting in order to further educate physician trainees who are sub-investigators on this study. Given physician time commitments we expect the nurse may perform a majority of the consenting herself. Patients who consent for participation will be randomized in a 1:1 ratio to one of two groups.

Group #1 – Fifteen patients will receive a suspension with the equivalent of one DS TMP-SMX by mouth every 12 hours.

Group #2 – Fifteen patients will receive a suspension with placebo by mouth every 12 hours.

Randomization will be generated by biostats and sealed envelopes will be held by [name] in the Research Pharmacy to be opened when a patient is recruited. [name] is the only one who will be unblinded and, in case of an emergency, he can break the blind at the request of one of the attending physician investigators.

The Intervention

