Upon consent patients will be given the COPD Assessment Test (CAT) (<https://www.mdcalc.com/copd-assessment-test-cat>), a validated scoring system used in COPD patients to assess progression, functional status, and effectiveness of pulmonary rehabilitation.[29–32] Participants will be monitored daily while in the hospital for highest oxygen need, need for non-invasive or invasive mechanical ventilation, and adverse events, daily monitoring will be carried out by the nurse coordinator. Medications used for the treatment of COPD and antibiotics used will be collected retrospectively for each patient. If the patient remains hospitalized at end of therapy, 30 days, or 90 days then follow up will occur in the hospital. Otherwise, the patient will be asked to come to the Infectious Diseases Clinical Research Office for follow up visits at end of therapy (+0-3 days to allow for schedule issues and end of therapy falling on a weekend), 30 days +/- 5 days, and 90 days +/- 10 days. A \$30 stipend will be paid to the participants after each follow up visit. At the end of treatment visit, the medication diary will be collected. At each follow up visit, the nurse coordinator will review the patient's need for oxygen, their medications for the treatment of COPD, any need to see a physician or go to an urgent care or an emergency room for COPD, and any admission to the hospital for COPD. The CAT will be administered at each follow up visit. An expectorated sputum sample will be collected at each follow up visit which will be transported to the Infectious Diseases Research Laboratory for analysis; sputum samples will be processed and analyzed with the Unyvero LRT system for presence of PJ by PCR. The schedule of events for

[figure not shown]

Figure 1: Schedule of Events

the study is shown in figure 1.

Statistical analysis

No formal power analysis was performed, the sample size of 15 patients per arm is felt to be appropriate for a pilot study and appropriate to the funding for this application. We expect to find enough cases of PJ colonization to identify and recruit the 30 patients to be included in the study from the pool of patients for the EPIC study.

Time to return to baseline O2 requirements, and time to next admission for exacerbation will be analyzed using cox proportional hazards regression or other ~~more appropriate time~~ time-to-event analysis method. Need for mechanical

IRB APPROVAL DATE: 06/08/2022

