ventilation will be analyzed using logistic regression. LOS will be analyzed using quantile regression. The number of urgent care/emergency room visits and number of hospitalizations for AECOPD within 3 months and mortality will be analyzed using Poisson regression (or other appropriate method if there is evidence of overdispersion). Durability of decolonization, change in medications for COPD, and CAT score will be a longitudinal analysis. This analysis plan was developed by [name] in Biostatistics who will perform the analysis.

Any participants who withdraw prior to the EOT assessment will be dropped from the study and replaced. Any participants who withdraw after completing the EOT assessment will be analyzed in a modified intent to treat population and not replaced. Only participants who complete all assessments will be analyzed as per protocol.

Anticipated Outcomes

We anticipate treatment of PJ colonized AECOPD patients with standard of care plus TMP-SMX will improve symptoms, decrease LOS and increase the interval free of acute exacerbations above standard of care alone. Using the CAT, we expect to have a quantifiable score which can demonstrate a difference in outcomes between the two groups.

We also anticipate that patients with AECOPD who are colonized with PJ and treated with standard of care alone will maintain colonization over the 3-month period of follow up. Patients who are treated with TMP-SMX in addition to standard of care are expected to have microbiological eradication of PJ colonization and we expect that eradication to last through the 3-month follow up visit.

Potential problem areas and alternative tactics

This study is relatively simple and straight forward, we do not anticipate any issues with identifying or recruiting patients for the study but recognize that recruitment can be lower than expected for any study.

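### No rule covers death or hospice discharge in length of stay and the time-to-event outcomes, so an early death can pass as a short stay

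*Combined protocol and SAP*

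**What the plan says.** The Statistical analysis section names a method for each outcome:

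- **LOS:** "LOS will be analyzed using quantile regression". The quantile is not named.
- **Time to next admission:** "time to next admission for exacerbation will be analyzed using cox proportional hazards regression", with another time-to-event method allowed. The same sentence covers time to return to baseline oxygen. No time origin, censoring rule or competing-event rule is given.
- **Death:** "mortality will be analyzed using Poisson regression", as a separate outcome.

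Specific Aims (Aim 1) sets the readmission window: "time to next admission for AECOPD and number of readmissions for AECOPD in the following 3 months". The Evaluations section foresees very long stays: "If the patient remains hospitalized at end of therapy, 30 days, or 90 days then follow up will occur in the hospital". That settles where the visit takes place, not how LOS or readmission is scored.

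The Statistical analysis section also says that anyone who withdraws before the end-of-treatment (EOT) assessment is removed and replaced. It does not say whether a death in that period counts as withdrawal. Anticipated Outcomes treats a shorter LOS and a longer exacerbation-free interval as benefit.

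**The concern.** LOS is a good outcome when short only if the stay ended in recovery. A patient who dies in hospital or leaves for hospice on day 2 has a recorded stay of 2 days, which sits at the favourable end of the LOS distribution. That patient also cannot have a later exacerbation admission. If one arm has more such exits, its LOS can look better because its patients did worse. A drug that prevented these exits could be penalised, and one that caused them rewarded.

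The separate mortality model would report the deaths, but it does not correct LOS or readmission, and hospice discharge has no model. With 15 patients per arm, possibly 10 (Potential problem areas and alternative tactics), two or three patients can move a median. The results are meant to support larger trials and grant applications, so the direction of a point estimate matters even without significance.

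**Working it through.** The plan has no power calculation, event rate or LOS distribution, so there is no figure of its own to reproduce on this point. The check asks how far the outcomes could move. Inputs marked (A) are assumptions.

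**1. Will such patients occur?** The chance of at least one death among 30 is 1 − (1 − p)^30, where p is the 90-day risk (A):

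- p = 2%: 0.6 expected, chance 45%
- p = 5%: 1.5 expected, chance 79%
- p = 10%: 3 expected, chance 96%

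For hospice, Clinical Relevance reports of the site's earlier PJ-positive patients that "the remaining 6 patients all had severe COPD and two of them were so severe that they entered hospice". That is 2 of 6, or 33% (exact 95% CI 4-78%). Table 1 excludes "Expected life span less than 3 months" and current ICU admission or ventilation, so the trial rate should be lower. The illustration uses 1 against 3 of 15 (A).

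**2. LOS, exits unrelated to the stay the patient would have had.** Stays are log-normal, median 5 days, log SD 0.6 (A), with k patients of 15 leaving by death or hospice on a fixed day. The arm median is the 8th smallest of 15 values. With k exits at the bottom, it is the (8 − k)th of the other 15 − k: the 7th of 14 for k = 1 and the 5th of 12 for k = 3. Scored as the longest stays, it is the 8th of 14 and the 8th of 12. Simulated mean medians:

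| Exit scored as | k = 1 | k = 3 | Difference (days) |
|---|---|---|---|
| day 2 | 4.84 | 4.24 | −0.60 |
| day 5 | 5.06 | 5.02 | −0.04 |
| day 8 | 5.36 | 6.09 | +0.73 |
| day 12 | 5.38 | 6.17 | +0.79 |
| longest stay | 5.38 | 6.17 | +0.79 |

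Over days 1 to 4 the difference runs from about −0.6 to −0.4 day. At day 2 the between-arm difference in medians has an SD of about 1.3 days.

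**3. LOS, exits among the patients who would have stayed longest.** With exit on days 1-4 (A) and 1 against 3 of 15, the worse arm's median is 0.77 day shorter as recorded, and that arm looks better in 77% of simulated trials. Scoring these exits as longest stays gives 0.00 day and 50%. With 1 against 2, the recorded shift is 0.41 day (64% of trials).

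**4. Time to next admission.** The documents say that "20-25% of cases lead to readmission within 30 days of discharge". At a constant hazard (A) the 90-day figures are 1 − 0.80³ = 49% and 1 − 0.75³ = 58%. The simulation has no treatment effect on readmission, a 90-day death risk of 6.7% v 20% (1 and 3 of 15), and a shared gamma frailty of variance 0, 1 or 2 (A). Hazard ratio (HR) for the arm with more deaths; the last column uses 15 per arm and 53% readmission:

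| Handling of death | HR | Trials with HR below 1 |
|---|---|---|
| Censored at death, independent risks | 1.00 | 50% |
| Censored at death, correlated risks | 0.95-0.97 | 53-55% |
| Admission-free to day 90 | 0.90-0.92 | 56-58% |
| Death or readmission as the event | 1.04-1.21 | 35-46% |

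**5. Time to baseline oxygen.** This was not simulated. Censoring at death treats the patient as someone who would have recovered at the same rate as those still observed, yet that patient can no longer recover.

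**The case against.** The strongest objection is that the plan is silent, not wrong. A reader might infer that it scores deaths and hospice discharges as short stays without readmission, but no sentence says so. A death on day 2 of a 10-day course cannot reach the EOT assessment. If it were handled as a withdrawal, the patient would be replaced and never enter the LOS model. The wording also allows another time-to-event method. This stands, and the point is limited to what can happen. But dropping early deaths would be another unstated choice that affects the result, so silence is no safeguard.

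The LOS bias also depends on timing, which the documents do not give. It needs exits before the typical stay, and the ICU and ventilation exclusion should make very early deaths uncommon. Even at day 2 the shift is less than half the SD of the difference. All of this stands.

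Three stronger readings are tempting and not supported:

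- **That a survivor who is never discharged also looks good on LOS.** That patient has a long stay, which counts against the arm. Only the impossibility of readmission applies.
- **That the readmission result changes sign.** Assume 40% readmission in general, 80% in two frail patients spared by treatment, and 1 v 3 deaths or hospice entries. Expected readmissions are then 12 × 0.4 + 2 × 0.8 = 6.4 in the better arm and 12 × 0.4 = 4.8 in the worse. Adding death and hospice gives 7.4 v 7.8. The reversal rests on the invented 80%, and raw counts are not the Cox analysis.
- **That 2 of 6 is the hospice rate to expect.** Those patients came from a different study, with neither the timing of hospice nor eligibility here reported.

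Finally, mortality is reported separately and the pilot admits it may not detect differences. That limits the consequence but does not make the LOS estimate interpretable.

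**Conclusion.** The gap is real and worth closing before unblinding. It is clearest for LOS, where an in-hospital death or hospice discharge before the typical stay, taken as recorded, counts as a good result. Under the assumed stays and 1 v 3 of 15, the worse arm's median looks about 0.4 to 0.6 day shorter for exits on days 1-4. There is almost no bias at day 5 and the reverse by day 8. The figure rests on the assumed stay distribution, exit days and split; none comes from the documents.

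For time to next admission the effect is smaller and conditional. Censoring at death does no harm if the risks are independent, and correlation moves the HR to 0.95-0.97. Only counting the dead as admission-free to day 90 brings it to 0.90-0.92. The documents do not support a claim that the planned analyses will favour the worse arm. They support the claim that nothing prevents it, and that the handling could be chosen after the data are seen.

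**What to change.** 1. **LOS:** name the median as the quantile, and score in-hospital death or discharge to hospice as longer than the longest observed stay. The median stays estimable while fewer than half of an arm (at most 7 of 15) is affected.
2. **Time to baseline oxygen:** keep patients who die in the risk set as not recovered, instead of censoring them at death.
3. **Time to next admission:** state in advance whether the clock starts at discharge or at randomisation, since a clock from discharge leaves out patients who die in hospital or are never discharged. Keep the AECOPD-only analysis, and add AECOPD admission or death as a sensitivity analysis with the components listed.
4. **Early deaths:** state that death before the EOT assessment is an outcome, not a withdrawal to be replaced.

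**Cost:** SAP wording and a derived LOS variable, with no extra patients, visits or samples. Items 1 and 2 need the disposition at the end of the index admission and the date of death. Item 3 needs dates of death after discharge; mortality is already an outcome, but the plan does not name the source of those dates and should. The drawback is that LOS scored this way mixes death with duration, so deaths and hospice discharges should be listed by arm and LOS as recorded shown alongside.

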The causes of progression of COPD, especially in the absence of continued tobacco use, are incompletely understood and a significant area of need. One proposed trigger for progression and increased AECOPD is colonization with *Pneumocystis jirovecii* (PJ), a fungal pathogen best known for causing pneumonia in patients with HIV or other forms of immunosuppression. It has been found to be more prevalent in those with severe COPD, particularly AECOPD, but as a colonizer, not a cause of acute pneumonia. Several studies have linked this pathogen with progression of COPD, showing that PJ perpetuates an inflammatory and lung remodeling response, contributing to development of airway obstruction, emphysema and accelerating the disease course.

Despite the overwhelming evidence that PJ contributes to the progression of COPD and to AECOPD, there have been no clinical trials to date on treating PJ in the context of COPD in review of the literature or documented on clinicaltrials.gov. The most likely explanation for this lack is the limited ability to detect PJ and the dependence on an invasive procedure, bronchoalveolar lavage, to obtain an appropriate sample. Currently we are studying the prevalence of PJ in this population of patients using a non-invasive, PCR based, sputum test for detection which will allow us to identify potential patients for a clinical trial. Our study aims to conduct a pilot prospective, randomized, double-blind, placebo-controlled treatment arm in hospitalized patients with AECOPD found to have PJ in their sputum, and without radiographic evidence of pneumonia. We will compare standard of care treatment plus trimethoprim-sulfamethoxazole vs placebo. Outcomes to be assessed are time to return to baseline oxygen, length of stay, need for mechanical ventilation, AECOPD free interval, readmissions to the hospital within 3 months, and clearance of PJ from end of treatment through 3 months.

Data obtained from this pilot study can be utilized to design a larger future clinical trial for the treatment of AECOPD as well as a larger prophylactic study on prevention of COPD progression and AECOPD using the paradigm of prophylaxis of PJ which has been so successful in the HIV population. This study addresses the gaps in current knowledge on the clinical significance of PJ in COPD patients and the management of COPD could potentially be revolutionized if treatment or prevention of PJ proves successful.

SPECIFIC AIMS

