By identifying patients colonized with PJ in the EPIC study, we will carry the cost of screening for the TOPIC study in the EPIC study, which allows the funding for this study to bear other needed expenses and make it feasible. The key personnel for the EPIC study overlap completely with the TOPIC study. We aim to enroll 30 patients but if we will have difficulties in recruiting, we may need to decrease the number of patients in the treatment group to 10 in each arm. Having a stipend for follow up visits will help with recruitment as will having [name], the director of Pulmonary Rehabilitation, as an investigator.

It is possible that we may see clinical improvement in the TMP-SMX group without microbiologic eradication. This could be due to TMP-SMX incompletely killing the PJ, we could have chosen a sub-optimal dose for the study, or it could be that the high sensitivity of PCR and the ability to detect dead organisms will work against us and we could still detect the organisms even if all were killed. Checking for colonization again at 30 days and at 90 days may be able to reveal this as dead organisms are cleared from the respiratory tract. It may be that it will take a longer trial to actually show microbiologic clearance even in the setting of clinical benefit.

This is a pilot study and, since we will have a small number of patients, we may not be able to detect statistically significant differences between the two groups, however by selecting the known PJ colonized patients for the study we are increasing the chances of being able to show a difference between the groups.

Potential for continuing this study with additional extramural funding

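### If one arm has no ventilation or no death, the stated logistic and Poisson models give no finite ratio estimate or usable Wald interval, and the plan names no method for that case

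*Combined protocol and SAP*

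**What the plan says.** In the Statistical analysis section of the combined protocol and SAP, need for mechanical "ventilation will be analyzed using logistic regression". No alternative is given. The same paragraph puts deaths together with counts of visits and admissions: "number of hospitalizations for AECOPD within 3 months and mortality will be analyzed using Poisson regression". The only fallback there is "or other appropriate method if there is evidence of overdispersion". The section's other open-ended wording, which allows a different time-to-event method, applies only to time to baseline oxygen and time to next admission.

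The sample size is 15 per arm, and "No formal power analysis was performed". The section on potential problem areas allows a reduction to 10 per arm if recruitment is slow.

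The ventilation outcome is described in two ways. The Aim 1 rationale lists "need for mechanical ventilation during the index admission". The Evaluations section has the coordinator record "need for non-invasive or invasive mechanical ventilation" each day. The plan does not say which of these is analysed.

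The opening summary gives the pilot's purpose: "Data obtained from this pilot study can be utilized to design a larger future clinical trial for the treatment of AECOPD".

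**The concern.** Both models estimate a ratio on the log scale. If one arm has no events, the likelihood keeps improving as the log ratio moves toward infinity, so there is no finite estimate and the Wald standard error means nothing. If both arms are empty, the data carry no information on the ratio. The overdispersion clause does not cover this, because an empty arm is not overdispersion. Nor does that clause apply to the logistic model.

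The eligibility criteria make low counts foreseeable. Patients in ICU or already ventilated are excluded, as are those expected to live less than 3 months. Ventilation is counted only during the index admission.

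What is at stake is the estimate. A pilot that feeds a larger trial should hand on an effect size with an interval. In this case the named models supply neither a finite effect nor a two-sided interval, and the replacement method would be chosen after the counts were known.

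**Working it through.** **Inputs.** From the documents: 15 per arm (Statistical analysis), possibly 10 per arm (Potential problem areas), 1:1 allocation (Patients), and the models above. Assumed, because the documents give no rates: event risks p of 5, 10, 15 and 20%, equal in the two arms. The sample size has no calculation behind it, so there is no plan figure to reproduce.

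**Step 1: chance of an empty arm.** One arm of n patients is empty with probability q = (1 − p)^n. At least one arm is empty with probability 1 − (1 − q)². Both are empty with probability q².

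Example, n = 15 and p = 5%: q = 0.95^15 = 0.463; at least one empty = 1 − 0.537² = 0.71; both empty = 0.463² = 0.21.

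| Risk per arm | At least one empty, 15 per arm | At least one empty, 10 per arm | Both empty, 15 per arm | Both empty, 10 per arm |
|---|---|---|---|---|
| 5% | 71% | 84% | 21% | 36% |
| 10% | 37% | 58% | 4% | 12% |
| 15% | 17% | 35% | 0.8% | 4% |
| 20% | 7% | 20% | 0.1% | 1% |

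With unequal risks of 10% and 5%, at least one arm is empty in 57% of trials at 15 per arm and 74% at 10 per arm.

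**Step 2: what the stated models return.** Arm-only models were fitted by maximum likelihood to 0/15 v 2/15, stopping after 10, 25 and 100 iterations.

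- Logistic log odds ratio: −9.7, −24.7, −34.7, with standard errors 51, 91,951 and 13.6 million.
- Poisson log rate ratio: −11.4, −26.4, −34.4, with standard errors 127, 230,170 and 12.6 million.

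The output depends on when the software stops. With 0/15 v 0/15, the logistic fit returned an arbitrary zero with a standard error that grew without limit, and the Poisson fit failed.

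**Step 3: what the likelihood still gives.** With one empty arm, inverting the 5% likelihood-ratio test gives an upper limit only. At 0/15 v 3/15 the limit is 0.80 for the odds ratio. For the Poisson rate ratio with k events in the other arm and equal exposure, the limit is exp(3.84 / 2k) − 1; with k = 3 this is exp(0.640) − 1 = 0.90. At 0/15 v 2/15 the limits are 1.53 and 1.61. With both arms empty there is no limit on a ratio.

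**Step 4: what a risk difference gives.** Newcombe's interval combines the two Wilson intervals and exists for every table. The difference is the empty arm minus the other arm.

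- 0/15 v 3/15: the Wilson intervals are 0 to 20.4% and 7.0 to 45.2%. Lower limit: −20 − √[(0 − 0)² + (45.2 − 20)²] = −45 points. Upper limit: −20 + √[(20.4 − 0)² + (20 − 7.0)²] = +4 points.
- 0/15 v 0/15: 0 points, −20 to +20.
- 0/10 v 0/10: 0 points, −28 to +28.

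The mean width over equal risks of 5 to 20% is about 46 to 55 points at 15 per arm and 59 to 67 at 10 per arm.

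**Step 5: do the candidate methods agree?** At 0/15 v 4/15 the Newcombe interval is −52 to −1 points and the Firth odds ratio is 0.08 with profile interval 0.0006 to 0.89. Both exclude no effect, while Fisher's exact p is 0.10. Adding a Fisher test to these intervals can therefore produce a conflicting message.

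**The case against.** The strongest reply is that little is lost. The counts will be available, a risk difference can be worked out afterwards, and a biostatistician is assigned to the analysis. The anticipated outcomes are symptoms, length of stay and exacerbation-free interval. Mortality is not in the Aim 1 list. The plan already concedes that "we may not be able to detect statistically significant differences between the two groups". Even with a better method the intervals are too wide to guide a larger trial much. All of this stands, and it sets the weight of the point. It does not remove the gap: the concession is about significance and is silent on an effect that cannot be estimated, and a repair made after seeing the counts is not pre-specified.

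Frequency is also unknown. The chance at 15 per arm falls from 71% to 7% across the assumed risks. If non-invasive ventilation counts as an event, the problem may be rare for ventilation. That stands too.

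Two stronger readings are tempting, and the documents do not support them. A reader might infer that an empty arm leaves no interval of any kind. Step 3 shows that a one-sided likelihood limit survives when only one arm is empty; the plan names no interval method, so it neither secures nor rules out that limit. A reader might also infer that the stated model would manufacture significance, since at 0/15 v 3/15 a logistic likelihood-ratio test gives p = 0.034 and Fisher's test 0.22. The plan names no test, alpha or decision rule, and the Wald p-value from the same model is close to 1, so that contrast says nothing definite about this plan.

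**Conclusion.** The point holds in a limited form. For ventilation and death, the named models have no finite maximum-likelihood estimate and no usable Wald interval when one arm is empty, and no ratio at all when both are. The plan has no rule for either case. Whether this is likely depends on event risks that the documents do not give: it is more likely than not at 5% risk at either sample size, and also at 10% risk with 10 per arm; at 20% risk with 15 per arm it is uncommon (7%). These figures assume equal risks and full arms of 15 or 10. For ventilation they also depend on an endpoint definition that is still open.

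The consequence is modest. This is an unpowered pilot with no decision rule, and it would lose a pre-planned estimate for two of several outcomes. A reader might go further and conclude that the pilot fails its purpose; the documents do not support that, since the raw counts remain reportable and the other outcomes are unaffected. It is a cheap improvement of low priority.

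**What to change.** Replace the stated models for these two outcomes with a short rule:

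1. For need for ventilation and for death, report events per arm and the risk difference with a Newcombe 95% interval as the single main result, labelled descriptive, whatever the counts.
2. Treat death as a binary outcome, and state how many participants have unknown 90-day vital status.
3. Keep Poisson regression, with its overdispersion clause, for visit and admission counts.
4. If an odds ratio is also wanted, use Firth-penalised logistic regression with its profile interval, labelled supplementary (0/15 v 3/15: 0.12, 0.0008 to 1.35). Do not add a separate Fisher test, for the reason in Step 5.
5. State whether non-invasive ventilation counts in the ventilation endpoint.

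The cost is a few sentences and no change to the visits or assessments. The downsides are that the intervals stay wide and these two outcomes have no formal test, which fits a pilot without a decision rule.
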